## 2.7.2 Protection Against Risks

The risks of side effects from medications will be mitigated by several mechanisms:

- As decreased renal function increases the risk of adverse effects of metformin and glibenclamide, renal function testing will be required prior to administration of medications for patients with a history of kidney disease and recommended for patients with hypertension and/or duration of diabetes of 10 years or greater. Glibenclamide and metformin will not be used for patients with eGFR <30 mL/min.

- Patients will be asked about adverse effects of metformin monthly. Patients who are taking glibenclamide
  will also be asked about hypoglycemia symptoms and medication will be down-titrated if these symptoms
  are present
- Patients above the age of 65 will have a less stringent treatment goal of A1c ≤8%, in accordance with ADA guidelines.
- Medication will only be up-titrated at 1 month checks when blood glucose is significantly above glycemic goals: FBG >180 mg/dL or PPBG >300 for patients below age 65 and FBG >200 mg/dL or PPBG >300 for patients 65 or older or with multiple comorbidities
- For aspirin use, patients will be asked about history of aspirin allergy in potentially emergent situations (when patient presenting with chest pain that could represent ACS) and aspirin will not be administered to patients with history of allergy. In non-emergent situations, patients will be asked both about history of allergy and signs of GI bleeding (blood in stool or black and tarry stools) prior to dispensing aspirin.

The risks of POC finger stick testing will be minimized by CHW training emphasizing sterile technique and standard precautions.

The risks posed by application malfunction or incorrect use will be mitigated by an intensive alpha testing process (systematically testing each possible scenario prior to implementation with patients to ensure correct

Version #: 1.0

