## Appendix 3 - Medication History, Side Effects, and Adherence

#### Medication History

- "Are you taking Metformin " (Y/N)
  - If NO, application skips to next question
  - If YES, "Are you only taking 1 pill size of Metformin " (Y/N)
    - If YES, "How many milligrams are the Metformin pills " (can select 500 mg, 850 mg, or 1000 mg, which are commonly available sizes in the area) and "How many Metformin pills do you take daily " (select from ½, 1, 2, 3, and 4)
    - If NO, "How many milligrams of Metformin do you take in total per day " (numeric entry box)
- "Are you taking Glibenclamide" (Y/N)
  - If NO, application skips to next question
  - If YES, "Are you only taking 1 pill size of Glibenclamide " (Y/N)
    - If YES, "How many milligrams are the Glibenclamide pills " (select 5 mg or 10 mg, the commonly available sizes in the area) and "How many Glibenclamide pills do you take daily " (select ½, 1, 2, 3, or 4)

<sup>7 These considerations are based on the Aspirin Guide clinical decision support tool, which provides guidance on the use of ASA in primary and secondary ASCVD prevention and is in turn based on guidance from the USPSTF

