#### [name]

- If NO, "How many milligrams of Glibenclamide do you take in total per day " (numeric entry box)
- "Are you taking any other medication for diabetes prescribed by a doctor " (Y/N)
- If NO, application skips to next question
  - If YES, application prompts promoter to enter medication name (free text), milligram strength of pills (numeric entry), and number of pills per day (½, 1, 2, 3, or 4)
- If patient not currently taking any medication, application prompts promoter to ask, "Have you previously taken medication for diabetes " (Y/N)
  - If YES, questions regarding medication side effects appear (These also appear if patient is taking any of the aforementioned medications)
  - If NO, application skips to the next section
  - "Are you currently taking medication for high blood pressure " (Y/N)
  - If YES
    - Application prompts promoter to collect information about name of medication (free text) and dosage (numeric entry)
    - Renal function testing will be recommended for this patient
    - Application skips to the next section
    - If NO, application skips to the next section

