# Appendix 4 - Hypoglycemia Protocol

# Protocol for identifying probable hypoglycemic episodes

- Patients who are taking glibenclamide are asked the following questions:
  - "In the last month, have you had episodes of any of the following symptoms":
    - Confusion
    - Trembling
    - Feeling uncoordinated
    - Palpitations
    - Abnormal sweating
    - Abnormal anxiousness
  - Patients reporting episodes of any of these symptoms are asked the following questions and their answers are scored as noted:
    - "Did these symptoms come on gradually or did they start suddenly"
      - Gradually (0)
      - Suddenly (+1)
    - "Did these symptoms occur when you had not eaten for several hours or after strenuous physical activity"
      - Yes (+1)
      - No (0)
    - "Did these symptoms improve after eating something
      - Yes (+1)
      - No (0)
- Patient considered to have probable hypoglycemia if above answers total to 2 or more points

and because the original validation study used this standard as well, we define adherence as taking medication "Nearly all of the time" or "All of the time".

<sup>10 Glibenclamide functions as an insulin secretagogue and has a duration of action of ~24 hours. Thus, it is expected to have a relatively short-term effect on blood glucose and it is essential to know the timing of the last dose when interpreting and acting on a patient's blood glucose level.

<sup>1These symptoms were found to be the most highly correlated with experimentally-induced hypoglycemia.

 <sup>12 In general, the onset of hypoglycemia symptoms is rapid rather than gradual
  This question assesses for the association of symptoms with two common risk factors for hypoglycemia that are likely to be present in our population

[name]

- Patients who have 2 or more points are asked the following question: "When you had these symptoms, were you so confused or sleepy that someone else needed to help you eat or drink something with sugar "
  - If YES, this is considered as an episode of probable severe hypoglycemia
  - If NO, this is considered an episode of probable mild hypoglycemia

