#### 6.5≤ A1c ≤Tx goal

- Not taking medications or nonadherent, no hypoglycemia or hypoglycemia symptoms, no problems with metformin → metformin 1700 mg
- Not taking medications or nonadherent, no hypoglycemia or hypoglycemia problems, problems with metformin
  - a. Agrees to take metformin  $\rightarrow$  metformin 850 mg
  - b. Refuses to take metformin → glibenclamide 2.5
- 3. Not taking medications or nonadherent, hypoglycemia or hypoglycemia symptoms, problems with metformin
  - a. Agrees to take metformin  $\rightarrow$  metformin 850 mg
  - b. Refuses to take metformin, prescribed glibenclamide >2.5 mg  $\rightarrow$  glibenclamide 2.5 mg
  - e. Refuses to take metformin, prescribed glibenclamide 2.5 mg  $\rightarrow$  MD consult
- 4. Taking metformin without problems
  - a. Metformin 500-1000 mg  $\rightarrow$  metformin 850 mg
  - b. Metformin 1500-2550 mg  $\rightarrow$  metformin 1700 mg
- 5. Taking metformin with problems
  - a. Metformin 500-850 mg, agrees to take metformin  $\rightarrow$  metformin 850 mg
  - b. Metformin 500-850 mg, refuses to take metformin  $\rightarrow$  glibenclamide 2.5 mg
  - c. Metformin 1000-1700 mg  $\rightarrow$  metformin 850 mg
  - d. Metformin 2000-2550 mg  $\rightarrow$  metformin 1700 mg
- 6. Taking glibenclamide without problems
- a. All doses  $\rightarrow$  metformin 1700 mg
- 7. Taking glibenclamide without problems, previous problems with metformin
  - a. Willing to take metformin
    - i. Glibenclamide 2.5 mg  $\rightarrow$  metformin 850 mg
    - ii. Glibenclamide 5 mg  $\rightarrow$  metformin 850 mg + glibenclamide 2.5 mg
    - iii. Glibenclamide 10 mg  $\rightarrow$  metformin 850 mg + glibenclamide 5 mg
    - iv. Glibenclamide 15-20 mg  $\rightarrow$  metformin 850 mg + glibenclamide 10 mg
  - b. Refuses to take metformin
    - i. Glibenclamide 2.5-10 mg → continue current dose of glibenclamide
  - ii. Glibenclamide 15-20 mg  $\rightarrow$  glibenclamide 10 mg
- 8. Taking glibenclamide with hypoglycemia or hypoglycemia symptoms

Version #: 1.0

[name]

- a. All doses  $\rightarrow$  metformin 1700 mg
- 9. Taking glibenclamide with hypoglycemia or hypoglycemia symptoms, previous problems with metformin a. Agrees to take metformin
  - i. Glibenclamide 2.5-5 mg  $\rightarrow$  metformin 850 mg
  - ii. Glibenclamide 10 mg  $\rightarrow$  metformin 850 mg + glibenclamide 2.5 mg
  - iii. Glibenclamide 15 mg  $\rightarrow$  metformin 850 mg + glibenclamide 5 mg

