#### Tx goal< A1c <9

- Not taking medications or nonadherent, no hypoglycemia or hypoglycemia symptoms, no problems with metformin → metformin 1700 mg
- 2. Not taking medications or nonadherent, no hypoglycemia or hypoglycemia symptoms, problems with metformin
  - a. Agrees to take metformin  $\rightarrow$  metformin 850 mg + glibenclamide 2.5 mg
  - b. Refuses to take metformin  $\rightarrow$  glibenclamide 2.5 mg
- 3. Not taking medications or nonadherent, hypoglycemia or hypoglycemia symptoms → metformin 1700 mg
- 4. Not taking medications or nonadherent, hypoglycemia or hypoglycemia symptoms, problems with metformin
  - a. Agrees to take metformin  $\rightarrow$  metformin 850 mg
  - b. Refuses to take metformin, prescribed glibenclamide >2.5 mg  $\rightarrow$  glibenclamide 2.5 mg
  - c. Refuses to take metformin, prescribed glibenclamide 2.5 mg  $\rightarrow$  MD consult
- 5. Taking metformin without problems
  - a. Metformin 500-1000 mg  $\rightarrow$  metformin 1700 mg
  - b. Metformin 1500-2000 mg → metformin 2550 mg
  - c. Metformin 2550 mg  $\rightarrow$  metformin 2550 mg + glibenclamide 2.5 mg
- 6. Taking metformin with problems
  - a. Metformin 500-850 mg, agrees to take metformin → metformin 850 mg + glibenclamide 2.5 mg

[name]

- b. Metformin 500-850 mg, refuses to take metformin  $\rightarrow$  glibenclamide 2.5 mg
- c. Metformin 1000-1700 mg  $\rightarrow$  metformin 850 mg + glibenclamide 2.5 mg
- d. Metformin 2000-2550 mg  $\rightarrow$  metformin 1700 mg + glibenclamide 2.5 mg
- 7. Taking glibenclamide without problems
  - a. Glibenclamide 2.5-10 mg  $\rightarrow$  metformin 1700 mg + glibenclamide current dose
  - b. Glibenclamide 15-20 mg → metformin 1700 mg + glibenclamide 10 mg
- 8. Taking glibenclamide, previous problems with metformin
- a. Agrees to take metformin
  - i. Glibenclamide 2.5-10 mg  $\rightarrow$  metformin 850 mg + glibenclamide current dose
  - ii. Glibenclamide 15-20 mg  $\rightarrow$  metformin 850 mg + glibenclamide 10 mg
  - b. Refuses to take metformin
    - i. Glibenclamide 2.5 mg  $\rightarrow$  glibenclamide 5 mg
    - ii. Glibenclamide 5 mg  $\rightarrow$  glibenclamide 10 mg
- iii. Glibenclamide 10-20 mg  $\rightarrow$  glibenclamide 10 mg
- 9. Taking glibenclamide with hypoglycemia or hypoglycemia symptoms
  - a. Glibenclamide 2.5 mg  $\rightarrow$  metformin 1700 mg
  - b. Glibenclamide 5 mg  $\rightarrow$  metformin 1700 mg + glibenclamide 2.5 mg

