#### 9≤ A1c ≤14

- 1. Not taking medications  $\rightarrow$  metformin 1700 mg + glibenclamide 2.5 mg
- 2. Not taking medications, problems with metformin
  - a. Agrees to take metformin → metformin 850 mg + glibenclamide 2.5 mg
  - b. Refuses to take metformin  $\rightarrow$  glibenclamide 2.5 mg
- 3. Not taking medications, hypoglycemia or hypoglycemia symptoms  $\rightarrow$  metformin 1700 mg
- 4. Not taking medications, hypoglycemia or hypoglycemia symptoms, problems with metformin
  - a. Agrees to take metformin, prescribed glibenclamide >2.5 mg  $\rightarrow$  metformin 850 mg + glibenclamide 2.5 mg
  - b. Agrees to take metformin, prescribed glibenclamide 2.5 mg  $\rightarrow$  metformin 850 mg
  - c. Refuses to take metformin, prescribed glibenclamide >2.5 mg  $\rightarrow$  glibenclamide 2.5 mg
  - d. Refuses to take metformin, prescribed glibenclamide 2.5 mg  $\rightarrow$  MD consult
- 5. Taking metformin without problems
  - a. Metformin 500-2000 mg  $\rightarrow$  metformin 1700 mg + glibenclamide 2.5 mg
  - b. Metformin 2550 mg  $\rightarrow$  metformin 2550 mg + glibenclamide 2.5 mg
- 6. Taking metformin with problems
  - a. Metformin 500-850 mg, agrees to take metformin  $\rightarrow$  metformin 850 mg + glibenclamide 2.5 mg
  - b. Metformin 500-850 mg, refuses to take metformin  $\rightarrow$  glibenclamide 2.5 mg
  - c. Metformin 1000-1700 mg  $\rightarrow$  metformin 850 mg + glibenclamide 2.5 mg
  - d. Metformin 2000-2550 mg  $\rightarrow$  metformin 1700 mg + glibenclamide 2.5 mg
- 7. Taking glibenclamide without problems
  - a. Glibenclamide 2.5-10 mg → metformin 1700 mg +glibenclamide current dose
  - b. Glibenclamide 15-20 mg  $\rightarrow$  metformin 1700 mg + glibenclamide 10 mg
- 8. Taking glibenclamide without problems, previous problems with metformin
  - a. Agrees to take metformin
    - i. Glibenclamide 2.5-10 mg → metformin 850 mg + glibenclamide current dose
    - ii. Glibenclamide 15-20 mg  $\rightarrow$  metformin 850 mg + glibenclamide 10 mg
  - b. Refuses to take metformin
    - i. Glibenclamide 2.5 mg  $\rightarrow$  glibenclamide 5 mg
    - ii. Glibenclamide 5 mg  $\rightarrow$  glibenclamide 10 mg
    - iii. Glibenclamide 10-20 mg  $\rightarrow$  glibenclamide 10 mg
- 9. Taking glibenclamide with hypoglycemia or hypoglycemia symptoms
  - a. Glibenclamide 2.5 mg  $\rightarrow$  metformin 1700 mg
    - b. Glibenclamide 5 mg  $\rightarrow$  metformin 1700 mg + glibenclamide 2.5 mg

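### At enrollment, former glibenclamide users off all medication are not scored for hypoglycemia symptoms, so Appendix 8 can restart the drug where its own symptom rows would not

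*Combined protocol and SAP*

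**What the plan says.** The symptom score is in Appendix 4, under the protocol for identifying probable hypoglycemic episodes. It covers the last month and opens: "Patients who are taking glibenclamide are asked the following questions". Section 2.7.2 states the same gate: glibenclamide takers "will also be asked about hypoglycemia symptoms and medication will be down-titrated if these symptoms" are present.

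Appendix 3 collects the glibenclamide pill size and daily dose only after a yes to "Are you taking Glibenclamide"; a no skips them. For someone on nothing there is one further step: "If patient not currently taking any medication, application prompts promoter to ask" whether diabetes medication was ever taken. A yes opens the side-effect questions. These are an open question, a structured follow-up on metformin gastrointestinal symptoms, and a free-text box for the physician. No past drug name, no past dose and no hypoglycemia score are recorded.

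Appendix 8 nevertheless has enrollment rows that use this information for patients off medication:

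- A1c 6.5 to goal, row 3: "Not taking medications or nonadherent, hypoglycemia or hypoglycemia symptoms, problems with metformin".
- A1c goal to 9, rows 3 and 4: "Not taking medications or nonadherent, hypoglycemia or hypoglycemia symptoms", without and then with metformin problems.
- A1c 9 to 14, rows 3 and 4: "Not taking medications, hypoglycemia or hypoglycemia symptoms", again without and then with metformin problems. Row 4 splits further by past dose, for example "Refuses to take metformin, prescribed glibenclamide 2.5 mg", which leads to a physician consult.

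**The concern.** The dosing table expects two inputs that the questionnaire does not supply for a patient who has stopped all medication: whether there were hypoglycemia symptoms, and what glibenclamide dose had been prescribed. With the symptom input absent, that patient is handled as symptom-free.

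The patient at stake stopped glibenclamide because it caused hypoglycemia symptoms. Followed as written, the application can hand the drug back at the enrollment visit. At A1c 9 to 14 with no metformin problem, row 1 (metformin 1700 mg plus glibenclamide 2.5 mg) is used instead of row 3 (metformin 1700 mg alone). If metformin is refused and the earlier dose was 2.5 mg, row 2b (glibenclamide 2.5 mg) is used instead of row 4d (physician consult). Section 2.7.1 itself names glibenclamide as the study drug most likely to do harm, and the safety of titration by community health workers is a stated objective.

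A separate, conditional issue concerns monthly visits. Appendix 9 tells patients to stop glibenclamide after an episode needing help until they see the health worker. If taking the drug is coded as current use, such a patient could miss the score at that visit. This would affect the secondary endpoint on hypoglycemia symptom prevalence and the capture of probable severe episodes. Appendix 10 has rows for patients who did not take the drug the day before, which suggests that prescribed use was meant there, so this part is not certain.

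**Working it through.** The plan gives no figure on this point, so the check is a branch-by-branch trace of Appendices 3, 4 and 8 for an enrollee off all medication who had hypoglycemia symptoms.

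**Pairing.** Each symptom-row output is set against the no-symptom (or default) row for the same A1c band and metformin status. Met = metformin, Glib = glibenclamide, doses in mg.

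| A1c band | Metformin status | Past Glib dose | Symptom row gives | Row actually reached gives | Differs |
|---|---|---|---|---|---|
| 6.5 to goal | problem, agrees | any | 3a: Met 850 | 2a: Met 850 | no |
| 6.5 to goal | problem, refuses | >2.5 | 3b: Glib 2.5 | 2b: Glib 2.5 | no |
| 6.5 to goal | problem, refuses | 2.5 | 3, third branch (printed e): physician consult | 2b: Glib 2.5 | yes |
| Goal to 9 | no problem | any | 3: Met 1700 | 1: Met 1700 | no |
| Goal to 9 | problem, agrees | any | 4a: Met 850 | 2a: Met 850 + Glib 2.5 | yes |
| Goal to 9 | problem, refuses | >2.5 | 4b: Glib 2.5 | 2b: Glib 2.5 | no |
| Goal to 9 | problem, refuses | 2.5 | 4c: physician consult | 2b: Glib 2.5 | yes |
| 9 to 14 | no problem | any | 3: Met 1700 | 1: Met 1700 + Glib 2.5 | yes |
| 9 to 14 | problem, agrees | >2.5 | 4a: Met 850 + Glib 2.5 | 2a: Met 850 + Glib 2.5 | no |
| 9 to 14 | problem, agrees | 2.5 | 4b: Met 850 | 2a: Met 850 + Glib 2.5 | yes |
| 9 to 14 | problem, refuses | >2.5 | 4c: Glib 2.5 | 2b: Glib 2.5 | no |
| 9 to 14 | problem, refuses | 2.5 | 4d: physician consult | 2b: Glib 2.5 | yes |

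**Count.** 1 of 3 + 2 of 4 + 3 of 5 = 6 of 12. In all six, glibenclamide 2.5 mg is dispensed where the symptom row gives none: three should have been metformin alone (850 mg twice, 1700 mg once) and three a physician consult.

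**Sensitivity to how branches are counted.** Four branches ignore past dose. Splitting each into 2.5 mg and above 2.5 mg gives 12 + 4 = 16 cells. Two of those four differ, so 6 + 2 = 8 of 16 differ, the same half.

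**Missing dose input.** Branches that depend on the prescribed dose: 2 (6.5 to goal) + 2 (goal to 9) + 4 (9 to 14) = 8 of 12. Even when a measured glucose below 70 mg/dL opens the symptom rows, these eight cannot be resolved for someone who answered no in Appendix 3.

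**Where the rows do work.** In the two lower bands the same rows also cover nonadherent users. They can answer yes to taking glibenclamide, be scored and have their dose recorded. The 9 to 14 rows name only patients not taking medication.

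**Possible pool.** The needs assessment in section 2.1 has 58% taking medication regularly, so 100 − 58 = 42 per 100 do not. That figure includes never-users and nonadherent users. It is at most a ceiling, and it assumes that enrollees resemble the assessed patients.

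**The case against.** The best reply is that taking was meant as prescribed. The off-medication rows split on a prescribed dose, which suggests they were written for people who hold a prescription and are not using it. If the Appendix 3 question is answered on that basis, those patients are scored and their dose is known. This helps the nonadherent user, but not the patient who has stopped: that patient answers no, and the no skips both the dose and the score.

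The second reply is that 6 of 12 overstates the reach, and part of this stands. Four of the six changed branches need a past dose of exactly 2.5 mg, while Appendix 3 lists 5 and 10 mg as the common tablets. Five of the six need a metformin problem, and three of those a refusal. Only row 3 of the 9 to 14 band applies without a metformin problem. For past doses above 2.5 mg, four symptom rows themselves allow a restart at 2.5 mg.

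The third reply points to safeguards: telephone advice, pairing with a coordinator in the first months, systematic testing of the application, the open side-effect question, and physician review. Each lowers the chance of harm, but none feeds the dosing row. Telephone advice depends on the health worker having a doubt. As printed, the free-text box appears only when the metformin gastrointestinal question is answered no, so it is not prompted in the five changed branches that involve a metformin problem. Review follows dispensing, within 1 to 2 days in section 2.7.1 but up to 1 week under Physician Oversight.

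Finally, the one-month recall means that widening the gate alone would reach only recent stoppers. That is correct, and the remedy has to reword the recall period.

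**Conclusion.** The concern holds. For an enrollee off all medication, the printed questionnaire does not supply the symptom and dose inputs that Appendix 8 uses. In 6 of 12 branches the result is glibenclamide 2.5 mg where the plan's own rule gives none. This rests on reading Appendices 3 and 4 literally and on symptoms being the only signal, with no glucose below 70 mg/dL at the visit.

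The number of patients affected cannot be derived from the documents and is probably well below the 42 per 100 ceiling. The restart is at the lowest dose. The four primary safety endpoints and the halting rule are not defined through the symptom score, so they are unaffected. The monthly-visit issue remains conditional. This should be fixed because the plan's own safety rows are unreachable for the patients they describe, but it does not threaten the main analysis.

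**What to change.** - In Appendix 4, put the symptom questions to anyone who was prescribed, dispensed, holding or had taken glibenclamide at any time in the last month. This also settles the monthly-visit ambiguity.
- In the Appendix 3 branch for patients who previously took diabetes medication, ask whether glibenclamide was one of them. If so, ask the Appendix 4 questions with the recall period worded as the time the patient was taking glibenclamide.
- In the same branch, record the last glibenclamide dose and the reason for stopping, so that the off-medication rows have their inputs before anything is dispensed.

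No dosing row changes. The cost is one skip-logic condition, one dose field with a reason for stopping, and about a minute of questioning for each former user.

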# Protocol for management of hypoglycemia detected with blood glucose testing during patient visit 1st glucose reading is <70

- Follow Up Question: "Is the patient unresponsive, very sleepy or confused "
  - YES: Unresponsive, very sleepy, or confused
    - Message: "Call a coordinator. The patient should be transported to the hospital immediately. The patient needs something with sugar (candy, juice, coke) immediately. If the patient is unable to drink something, sprinkle sugar under the tongue."
    - NO: Normal mental status
      - Message: "Blood sugar is low. Please re-test to confirm."
      - Re-test to confirm
- Promoter repeats blood glucose (reading 2)
  - Reading 2 ≥70
    - Message: "It is now in normal range. Continue with the questions."
  - Reading 2 <70

.

- Message: "It remains very low. The patient should eat something with sugar (candy, juice, coke) immediately". The app also provides a list of options for 15 grams of simple carbohydrate.
- Message: "Wait 15 minutes after eating and re-test."
- Re-test after eating and waiting 15 minutes
- Reading 2 ≥400
  - Message: "Drastic change. Please start over."
- Promoter repeats blood glucose (reading 3)
  - Reading 3 ≥70
    - Message: "It is now in a normal range. The patient should eat a full meal to prevent the blood sugar from dropping again. Continue with the questions after the patient has eaten."
    - Recommendation: "Be vigilant and seek medical attention if you begin to feel bad. You should have someone with you for the rest of the day"
    - Application will lower dosage of glibenclamide
    - Reading 3 <70
      - Message: "It remains very low. The patient should eat something with sugar (candy, juice, coke) immediately". The app also provides a list of options for 15 grams of simple carbohydrate.
      - Message: "Wait 15 minutes after eating and re-test."
      - Re-test after eating and waiting 15 minutes
- Promoter repeats blood glucose if indicated (reading 4)
  - Reading 3 ≥70

Version #: 1.0

.

<sup>14 Table sugar sprinkled under the tongue has been shown to be comparable to intravenous glucose for the treatment of severe hypoglycemia in two small studies performed in resource-limited settings

